ANNEX 6: VARIABLES TO BE USED IN DATABASES

Condition	ICD-9 Codes	Text
Abdominal Bloating	536.3	Gastroparesis
GERD	530.11	Reflux esophagitis
GERD	787.1	Heartburn
GERD	787.2	Dysphagia
GERD	787.20	Dysphagia, unspecified
GERD	787.21	Dysphagia, oral phase
GERD	787.22	Dysphagia, oropharyngeal phase
GERD	787.23	Dysphagia, pharyngeal phase
GERD	787.24	Dysphagia, pharyngoesophageal phase
GERD	787.29	Other dysphagia
IBS	555	Regional enteritis
IBS	555.0	Regional enteritis of small intestine
IBS	555.1	Regional enteritis of large intestine
IBS	555.2	Regional enteritis of small intestine with large intestine
IBS	555.9	Regional enteritis of unspecified site
IBS	556	Ulcerative colitis
IBS	556.1	Ulcerative (chronic) ileocolitis
IBS	556.3	Ulcerative (chronic) proctosigmoiditis
IBS	556.5	Left-sided ulcerative (chronic) colitis
IBS	556.6	Universal ulcerative (chronic) colitis
IBS	556.8	Other ulcerative colitis
IBS	556.9	Ulcerative colitis, unspecified
Nausea and Vomiting	78.82	Epidemic vomiting syndrome
Nausea and Vomiting	536.2	Persistent vomiting
Nausea and Vomiting	564.3	Vomiting following gastrointestinal surgery
Nausea and Vomiting	643	Excessive vomiting in pregnancy

Condition	ICD-9 Codes	Text
Nausea and Vomiting	643.2	Late vomiting of pregnancy, unspecified as to episode of care or not applicable
Nausea and Vomiting	643.2	Late vomiting of pregnancy
Nausea and Vomiting	643.21	Late vomiting of pregnancy, delivered, with or without mention of antepartum condition
Nausea and Vomiting	643.23	Late vomiting of pregnancy, antepartum condition or complication
Nausea and Vomiting	643.8	Other vomiting complicating pregnancy
Nausea and Vomiting	643.8	Other vomiting complicating pregnancy, unspecified as to episode of care or not applicable
Nausea and Vomiting	643.81	Other vomiting complicating pregnancy, delivered, with or without mention of antepartum condition
Nausea and Vomiting	643.83	Other vomiting complicating pregnancy, antepartum condition or complication
Nausea and Vomiting	643.9	Unspecified vomiting of pregnancy
Nausea and Vomiting	643.9	Unspecified vomiting of pregnancy, unspecified as to episode of care or not applicable
Nausea and Vomiting	643.91	Unspecified vomiting of pregnancy, delivered, with or without mention of antepartum condition
Nausea and Vomiting	643.93	Unspecified vomiting of pregnancy, antepartum condition or complication
Nausea and Vomiting	787.03	Vomiting alone
Nausea and Vomiting	787.0	Nausea and vomiting
Nausea and Vomiting	787.01	Nausea with vomiting
Nausea and Vomiting	787.02	Nausea alone
Orthostatic Hypotension	458.0	Orthostatic hypotension
Orthostatic Hypotension	780.2	Syncope and collapse
Orthostatic Hypotension	992.1	Heat syncope
Parkinson's	094.82	Syphilitic parkinsonism
Parkinson's	332	Parkinson's disease
Parkinson's	332.0	Paralysis agitans
Parkinson's	332.1	Secondary parkinsonism
Suppressed Lactation	676	Other disorders of the breast associated with childbirth and disorders of lactation
Suppressed Lactation	676.4	Failure of lactation
Suppressed Lactation	676.40	Failure of lactation, unspecified as to episode of care or not applicable
Suppressed Lactation	676.41	Failure of lactation, delivered, with or without mention of antepartum condition

Condition	ICD-9 Codes	Text
Suppressed Lactation	676.42	Failure of lactation, delivered, with mention of postpartum complication
Suppressed Lactation	676.43	Failure of lactation, antepartum condition or complication
Suppressed Lactation	676.44	Failure of lactation, postpartum condition or complication
Suppressed Lactation	676.5	Suppressed lactation
Suppressed Lactation	676.50	Suppressed lactation, unspecified as to episode of care or not applicable
Suppressed Lactation	676.51	Suppressed lactation, delivered, with or without mention of antepartum condition
Suppressed Lactation	676.52	Suppressed lactation, delivered, with mention of postpartum complication
Suppressed Lactation	676.53	Suppressed lactation, antepartum condition or complication
Suppressed Lactation	676.54	Suppressed lactation, postpartum condition or complication
Suppressed Lactation	676.8	Other disorders of lactation
Suppressed Lactation	676.80	Other disorders of lactation, unspecified as to episode of care or not applicable
Suppressed Lactation	676.81	Other disorders of lactation, delivered, with or without mention of antepartum condition
Suppressed Lactation	676.82	Other disorders of lactation, delivered, with mention of postpartum complication
Suppressed Lactation	676.83	Other disorders of lactation, antepartum condition or complication
Suppressed Lactation	676.84	Other disorders of lactation, postpartum condition or complication
Suppressed Lactation	676.9	Unspecified disorder of lactation
Suppressed Lactation	676.90	Unspecified disorder of lactation, unspecified as to episode of care or not applicable
Suppressed Lactation	676.91	Unspecified disorder of lactation, delivered, with or without mention of antepartum condition
Suppressed Lactation	676.92	Unspecified disorder of lactation, delivered, with mention of postpartum complication
Suppressed Lactation	676.93	Unspecified disorder of lactation, antepartum condition or complication
Suppressed Lactation	676.94	Unspecified disorder of lactation, postpartum condition or complication

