9.3.2. Indication

Indication will be estimated from the diagnoses recorded in the time period preceding each domperidone prescription:

- The indication for the prescription will be defined as nausea/vomiting if the subject has a recorded diagnosis classified as nausea or as vomiting, on the day of the prescription or in the preceding 7 days.
- For those prescriptions whose indication is not defined as nausea/vomiting, the indication will be defined as off-label if the subject has, in the 2 months up to and

including the date of domperidone prescription, a diagnosis classified as one of the following:

- o GERD;
- Abdominal bloating, gastric dysmotility, delayed gastric emptying;
- o IBS;
- Suppressed lactation, failed lactation, lactation not established, decreased lactation, lactation problem; or
- Orthostatic hypotension and a diagnosis of Parkinson's disease.
- For those prescriptions not classified as above, the indication will be classified as unknown.

For a list of the diagnostic terms and codes that will be used to identify the above conditions, see Annex 6.

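### Four of the 20 nausea/vomiting rows in Annex 6 have lost a zero, so exact text matching in the Spanish (ICD-9-CM) data would misclassify some on-label prescriptions as unknown or off-label

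*Protocol*

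**What the plan says.** Section 9.3.2 assigns each prescription's indication in order. It is nausea/vomiting if such a diagnosis is recorded on the day or in the 7 days before. Failing that, it is off-label if a listed off-label diagnosis falls in the 2 months up to and including the prescription date. For the rest: "For those prescriptions not classified as above, the indication will be classified as unknown". The section then points to the code list: "For a list of the diagnostic terms and codes that will be used to identify the above conditions, see Annex 6".

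Annex 6 prints that list under an ICD-9 heading. The relevant rows are:

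- "Late vomiting of pregnancy, unspecified as to episode of care or not applicable": 643.2, and the parent term is also 643.2.
- "Other vomiting complicating pregnancy, unspecified as to episode of care or not applicable": 643.8, and the parent term is also 643.8.
- "Unspecified vomiting of pregnancy, unspecified as to episode of care or not applicable": 643.9, and the parent term is also 643.9.
- "Epidemic vomiting syndrome": 78.82.
- For comparison, "Failure of lactation, unspecified as to episode of care or not applicable": 676.40, with parent 676.4.
- For comparison, "Syphilitic parkinsonism": 094.82.

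Section 9.7 counts an unknown indication as on-label in scenarios 1 and 3 and as off-label in scenarios 2 and 4. Annex 5 describes only the Spanish database as coded in ICD-9-CM. France, Germany and Belgium use ICD-10, and the UK uses Read codes. The protocol states no rule for matching codes.

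**The concern.** One code cannot be meant for two different terms, and one stem of two digits in a table of three-digit stems points to a lost digit. The damage lies only in the on-label group. A prescription whose sole nausea/vomiting record carries one of the intended codes may therefore go unrecognised, and no off-label row is damaged in a way that would offset this.

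What is at stake is the compliance proportion in scenarios 2 and 4 for Spain, which has its own primary risk ratio because Section 8.1 evaluates the statistic by country. The tabulation of apparent indications would also show too little nausea/vomiting and too much unknown. The printed list is the natural starting point for the ICD-10 and Read lists, so it should be right before anyone translates it.

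**Working it through.** **Row count (Annex 6).** There are 74 rows: 20 for nausea and vomiting, and 54 for all other conditions.

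- Nausea and vomiting: 20 rows but 17 distinct codes, because 643.2, 643.8 and 643.9 each appear twice (20 − 3 = 17).
- Other conditions: 54 rows and 54 distinct codes.
- Stems shorter than three digits: one in 74, namely 78.82.
- Final zeros kept elsewhere: 787.20, 676.40, 676.50, 676.80 and 676.90, each beside its parent, and also 555.0, 458.0, 332.0 and 787.0. Leading zero kept: 094.82.

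Damaged rows: 3 + 1 = 4 of 20 (20%), and 0 of 54. With the zeros restored (078.82, 643.20, 643.80, 643.90) the nausea/vomiting group has 20 rows and 20 distinct codes, and no other row changes.

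**Which intended codes the printed list would find.**

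| Intended code | Exact text | Listed code used as stem | Compared as numbers |
|---|---|---|---|
| 078.82 | missed | missed | found |
| 643.20 | missed | found (643, 643.2) | found |
| 643.80 | missed | found (643, 643.8) | found |
| 643.90 | missed | found (643, 643.9) | found |

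Exact matching is the natural reading of the annex. It lists parents and children separately (676.4 with 676.40 to 676.44; 787.2 with 787.20 to 787.24 and 787.29), and the child rows would be redundant under stem matching.

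**What happens to a missed prescription.** It stays in the denominator.

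- With no off-label diagnosis in the 2-month window it becomes unknown: still on-label in scenarios 1 and 3, non-compliant in scenarios 2 and 4.
- With such a diagnosis it becomes off-label under the Section 9.3.2 order.

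**Size.** Let p be the true compliance proportion in scenario 2 or 4. Let m be the share of compliant prescriptions whose nausea/vomiting is identified only by an affected code. Then

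observed compliance = p × (1 − m).

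The documents give no value for m, so the following are assumptions, with p = 30% (a baseline row of Table 2):

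- m = 1%: 0.30 × 0.99 = 29.7%
- m = 5%: 0.30 × 0.95 = 28.5%
- m = 10%: 0.30 × 0.90 = 27.0%

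The post/pre ratio is multiplied by (1 − m_post)/(1 − m_pre). With equal m this factor is 1, so a true ratio of 1.20 stays 1.20.

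**The case against.** The strongest reply is that this is a typing slip with little reach. No matching rule is stated, and the programming specification or the statistical analysis plan may set one. Each damaged row carries its full text, so a coder could see what was meant. Section 9.8 provides for validation of coding and independent review of programs. Only one of five databases uses ICD-9-CM. Most of this stands as a limit on size. It does not make the table correct, and Annex 6 is the reference against which a coding check would be made.

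Could the zeros have been lost when the PDF was read? This is unlikely, since the zeros in 787.20, 676.40, 555.0, 787.0 and 094.82 came through. A glance at the PDF settles it.

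A reader might also infer more than the documents support:

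- *That prescriptions are dropped.* They are reclassified and remain in the denominator.
- *That all four scenarios fail.* A prescription that is merely unknown still passes the indication condition in scenarios 1 and 3. One with a recent off-label diagnosis becomes off-label under Section 9.3.2. However, the wording of scenarios 2 and 4 in Section 9.7, read literally, excludes a recent GERD diagnosis even alongside nausea/vomiting, so the lost zero need not be what makes it fail there.
- *That all countries are affected.* The printed codes apply directly only to Spain. Carry-over to the translated lists is possible but not shown, because translation can work from the intact text.
- *That epidemic years would distort the pre/post ratio.* No frequency is given for any of these codes, and three of the four concern pregnancy.
- *That early-pregnancy vomiting is missing.* The annex lists the parent 643, and nothing in the document shows which subcodes exist beneath it.

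**Conclusion.** The error is real and minor. Four of 20 nausea/vomiting rows in the operative code list have lost a zero, and the list's own pattern shows it without an outside code book. Under exact text matching all four intended codes are missed. Under stem matching only the epidemic-vomiting code is missed, and under numeric comparison none is.

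The direction is fixed: reported compliance can only fall, mainly in scenarios 2 and 4 for Spain. The amount is unknown. It is probably small, because the general codes 787.0, 787.01, 787.02 and 787.03 are intact and only prescriptions with no other nausea/vomiting record in the 7-day window are exposed. The primary risk ratio is unaffected if the loss is equal in both years, and the documents give no reason to expect otherwise.

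The conclusion rests on exact matching, which the layout of the annex suggests but the protocol does not state.

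**What to change.** Before extraction, and before the list is translated to ICD-10 and Read codes:

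1. Change 78.82 to 078.82.
2. In the three rows whose text ends with the unspecified-episode phrase, change 643.2, 643.8 and 643.9 to 643.20, 643.80 and 643.90, keeping one parent row for each. Confirm all four against the code book when making the change.
3. Hold codes as text, so that zeros cannot be lost again.
4. State that matching is exact at the full code. Stem matching is not a safe substitute: it still misses 078.82, and the bare row 676, whose text also covers breast disorders associated with childbirth, would bring in every code beneath it as off-label lactation use.

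The cost is four cells and one sentence in an annex. No new data are needed and no other analysis changes.
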